### 3.12 Randomization

The patients will be randomly assigned in a 1:1 ratio to intervention or control group after the initial mapping and PVI using the Redcap web-based database system. Apart from the investigator, all health care professionals and the patient will be blinded to the allocation.

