## 1.0 Background

Atrial fibrillation (AF) is the most common sustained arrhythmia in adults with a lifetime risk of approximately 30%. AF significantly increases the risk of stroke, is associated with increased overall mortality and may impair quality of life. Treatments to effectively eliminate AF and maintain sinus rhythm may not only improve quality of life, but may even reduce mortality.

In patients with paroxysmal AF (PAF), AF has been found to be triggered by frequent ectopic atrial activity emerging from the pulmonary veins (PVs). Pulmonary vein isolation (PVI) has been developed to isolate the ectopic activity from initiating AF. PVI has proven efficient in patients with PAF with 1-year success rates up to 90%.

In patients with persistent AF (PsAF), data on a PV trigger-based initiation is not so clear, and the 1-year efficacy of pulmonary vein isolation only in this population is reported between 50-70% and significant lower as compared with patients with PAF. Furthermore, in patients having recurrence after PVI, a large proportion of patients with PsAF have isolated pulmonary veins at re-ablation. This indicates that patients with PsAF that have recurrence after PVI might benefit from ablation outside the pulmonary veins.

For some time, it has been assumed that in patients with PsAF there may be additive effect to PVI, by targeting the atrial substrate responsible for AF maintenance. However, the best method to characterize and target this so-called “substrate” remains elusive. The most commonly employed techniques for targeting the substrate used in the past were the creation of linear lesions across critical structures of the left atrium (LA), ablation of complex fractionated electrograms (CFAE), and targeting areas of low voltage detected by multipolar electroanatomical mapping.

The STAR AF II study showed that addition of either linear ablation or ablation of CFAE to PVI for PsAF did not offer any additional benefit over PVI alone. There was no significant difference in the results of the three strategies in terms of freedom from AF or any atrial arrhythmia. In fact, there seemed to be a weak trend towards better outcome with PVI alone. However, the STAR- AF II study included only de-novo procedures and in patients returning for re-do procedures, only 20% had isolated veins, indicating that durable block across the lines was achieved in a minority of this cohort.

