With updated approaches and technologies, including introduction of pulsed-field ablation, the efficiency of creating durable isolation of PVs has significantly increased over the last years. While PVI alone still remains the standard for the first ablation in patients with PsAF, the PVs are found to be isolated in a higher proportion of patients referred for re-do ablation. This shows that in these patients, PVI alone is not sufficient and revive the relevance of investigating the significance of targeting substrate outside PVs.

The VENUS study demonstrated the benefit of vein of Marshall (VOM) ethanol ablation in de novo ablation of PsAF. Furthermore, preliminary results of the Marshall plan study suggest the benefit of VOM ethanol ablation in combination with block of mitral and tricuspid isthmus and dome line, also in de novo ablation of PsAF. Whether this strategy improves outcome in patients with PsAF undergoing re-ablation where the need for extrapulmonary ablation might be higher has not been tested in a randomized study We aim to investigate,

if the addition of VOM ethanol ablation in combination with block of mitral and tricuspid isthmuses and dome line to PV re-isolation will improve the results of re-ablation of PsAF.

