### 3.2 Study design

This study is a prospective, patient and assessor blinded, 1:1 randomized superiority trial. Consecutive patients referred for re-ablation of symptomatic PsAF after previous PVI will be included. All preoperative procedures will be conducted according to the department's standard operational procedures for AF ablation. In all patients, an electro anatomical map (CARTO™, Biosense Webster, Diamond Bar, CA, or EnSite X™, Abbott Laboratories, Abbott Park, IL) of the LA with a multipolar mapping catheter (PENTARAY™ or OCTARAY™, Biosense Webster, Diamond Bar, CA, or Advisor™ HD Grid, Abbott Laboratories, Abbott Park, IL) will be constructed and reconnection of PVs will be assessed in sinus rhythm. If reconnection is present, re-PVI will be performed and confirmed with the multipolar mapping catheter. Patients in atrial fibrillation will undergo cardioversion to sinus rhythm prior to mapping. After mapping and confirming isolation of the PVs, patients will be randomized using the Redcap Database software to intervention or control. The intervention group will undergo VOM ethanol ablation including supplementary LA and coronary sinus ablation, if needed to achieve mitral isthmus block plus creation of dome line and cavotricuspid isthmus (CTI) block according to section 3.7. VOM ablation, mitral and CTI ablation and dome line will not be performed in control group and patients in control group will undergo no further ablation. The energy source used will be radiofrequency ablation or pulsed field ablation, at the discretion of the physician. However, radiofrequency should be preferred near coronary arteries. For dome line, focal PFA is preferred. All post-procedural work-up and follow-up will be the same for both randomization groups and assessment of outcomes will be performed by personnel blinded to randomization.

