#### 2: Intervention

Control group:

- Programmed atrial stimulation (4 extra stimuli (ES) at 350 ms baseline cycle length (CL), with simultaneous decrement of all four ES down to refractory period). If AFL or AF will not be induced with programmed atrial stimulation, then burst pacing (5 s bursts with 10 ms decrement between bursts, starting from CL 300 ms down to 180 ms), will be performed. Mean CL of AF will be measured in left and right appendage. If AFL is induced, this is mapped using a combination of activation and entrainment mapping, but will not be ablated. Patients will be cardioverted to sinus rhythm and no additional ablation will be performed.

Intervention group:

- CTI block and VOM ethanol injection will be performed. Mitral isthmus block will be completed with endocardial and, if necessary, epicardial ablation in coronary sinus followed by dome line. Order of the ablation lines will be performed at the discretion of the physician. Programmed atrial stimulation will be performed as described above, and if AFL or AF will not be induced, then burst pacing will be performed as described above. In case of AF, mean CL will be measured in left and right appendage. No additional mapping or ablation of AF will be performed and the patient will be cardioverted. If AFL is induced, this is mapped and ablated using a combination of activation and entrainment mapping. Afterwards, induction will be performed again until AFL is not inducible anymore. If AF will be induced two times in a row, AF will be cardioverted and the procedure ended. The procedure is ended earlier on the discretion of the operator or if induced AFL is judged non-clinical. All the lines will be checked at the end of procedure for bidirectional block according to the respective institution's standard and a waiting time after the last ablation at a line will be 30 minutes.

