## 4.0 RECRUITMENT OF PARTICIPANTS

### 4.1 Consent to participate

As normal clinical praxis, all patients scheduled for AF ablation are seen in the out-patient-clinic 4-6 weeks before the procedure where the medical history is clarified, CT scanning is done and the patients receive information about the procedure. Patients referred to redo procedures for AF (approximately 200 patients) are screened to identify candidates that comply to the inclusion and exclusion criteria. Following information in patient record is used for this screening: age, frequency, symptomatology and duration of AF episodes during the last year, previous ablation procedures and concomitant diseases. This information will be found in the medical record from the last year. This information will be passed-on to the project. Potential candidates will be approached by a study dedicated nurse and under undisturbed conditions, she will provide oral and written information about the study. Written consent form may be signed at this time, later during the day or on the day of the procedure. This ensures that the patient has sufficient time (at least >48 hours) to consider participation and to discuss this with relatives if desired. Another meeting with participation of relatives can be arranged. At any time, participants may withdraw their consent without having to give a reason for this. Patients who decide not to join the study will receive treatment according to current best clinical practice.

Normally, inclusion of 180 patients in the three participating centers will last less than a year.

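### Section 3.12 names no stratification factor, although there are three centres and pulmonary vein status, known before allocation, decides whether a control patient has any ablation

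*Protocol*

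**What the plan says.** **Allocation.** Protocol section 3.12: "The patients will be randomly assigned in a 1:1 ratio to intervention or control group after the initial mapping and PVI", through REDCap. Neither this section nor any other mentions stratification, blocks or minimisation. Section 4.1 expects that "inclusion of 180 patients in the three participating centers will last less than a year".

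**Order of events.** Section 3.2: "After mapping and confirming isolation of the PVs, patients will be randomized using the Redcap Database software to intervention or control". Re-isolation before that step is conditional: "If reconnection is present, re-PVI will be performed and confirmed with the multipolar mapping catheter".

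**Control arm after allocation.** Section 3.2: "patients in control group will undergo no further ablation". Section 3.7 adds that flutter induced in a control patient is mapped but not ablated: "Patients will be cardioverted to sinus rhythm and no additional ablation will be performed".

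**How common isolated veins are.** Section 1.0 says that among patients with recurrence after PVI, "a large proportion of patients with PsAF have isolated pulmonary veins at re-ablation", and that with newer techniques "the PVs are found to be isolated in a higher proportion of patients referred for re-do ablation". It gives no percentage for the population of this trial.

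**Analysis.** Section 3.11 plans a Student t-test on the change in AFEQT. Baseline variables enter the comparison only if the arms turn out to differ on them. The parameters listed in section 3.6 do not include PV reconnection at the index mapping.

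**The concern.** Taken together, sections 3.2 and 3.7 mean that a control patient with a reconnected vein has re-isolation, while a control patient whose veins are all isolated has mapping, stimulation and, where needed, cardioversion, but no ablation. Section 1.0 gives durable vein isolation as the reason to look for benefit outside the veins. PV status is therefore a natural candidate to modify the treatment effect, and it is available at the moment of the REDCap call.

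Centre is the other obvious factor. Section 3.2 allows two mapping systems and leaves the energy source to the physician, and section 3.7 has block checked by each institution's own standard.

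At stake are chance imbalance on either factor and some precision. The safeguard in section 3.11 depends on the observed data, and it can act on PV status only if PV status is recorded, which section 3.6 does not provide for.

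The allocation scheme has to be fixed before the first patient is randomised, and section 3.12 is where it belongs. A later SAP cannot supply design strata.

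**Working it through.** **1. The plan's own figure.** Inputs from the power calculation in section 3.4: difference 10, SD 20, power 90%, alpha 5% (taken as two-sided).

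n per arm = 2 × (1.960 + 1.282)² × 20² / 10² = 84.06. Rounded up this is 85 per arm, or 170. At 84 per arm (168 in total) power is 90.0%, so the stated 168 is reproduced.

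**2. Chance imbalance in PV status.** Assumptions: unrestricted allocation, 90 per arm (180/2), and a share q of patients with all veins isolated. The protocol gives no q, so a range is shown.

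SD of the between-arm difference in shares = √(q(1 − q) × 2/90).

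| q | SD | P(difference > 10 points) | P(difference > 15 points) |
|---|---|---|---|
| 0.2 or 0.8 | 0.060 | 9% | 1% |
| 0.3 or 0.7 | 0.068 | 14% | 3% |
| 0.5 | 0.075 | 18% | 4% |

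**3. Effect on the estimate.** Shift = imbalance × difference in mean AFEQT change between PV strata. That difference is assumed to be 5 to 10 points; the protocol gives none.

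- 0.10 × 5 = 0.5 and 0.10 × 10 = 1.0
- 0.15 × 5 = 0.75 and 0.15 × 10 = 1.5

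The shift is therefore 0.5 to 1.5 points against a target of 10.

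**4. Precision gained by a model term for PV status.** Residual SD = √(400 − g² q(1 − q)), where g is the difference between strata.

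- For g = 5 to 10 and q = 0.3 to 0.5, the residual SD is 19.4 to 19.9.
- Power at 84 per arm is then 90.4 to 91.7%, against 90.0% without the term. The N needed is 158 to 166.
- Example with g = 8, q = 0.5: variance explained = 64 × 0.25 = 16, and 16/400 = 4%. The 95% CI half-width falls from 1.96 × 20 × √(2/84) = 6.05 to 1.96 × 19.6 × √(2/84) = 5.93 points, about 2%.

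**5. Centre.** Assume three equal centres of 60 and unrestricted allocation. A split of 35:25 or worse has probability 0.245 in a given centre, and 1 − (1 − 0.245)³ = 0.57 in at least one of three. No effect on the estimate can be computed, because the protocol gives nothing on differences between centres.

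**6. Power within one PV stratum.** For a 10-point effect with SD 20 and 168 evaluable patients:

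| Share in stratum | Per arm | Power |
|---|---|---|
| 30% | 25 | 42% |
| 50% | 42 | 63% |
| 70% | 58 | 77% |

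Stratified allocation does not change these values.

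**The case against.** The case on the other side is substantial, and most of it stands.

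- **Silence is not a statement.** Section 3.12 never says that allocation is simple or unrestricted, and strata or blocks may exist in the REDCap set-up. This stands. The point is that none is specified, and the imbalance probabilities above apply only if allocation is unrestricted.
- **No bias.** Simple 1:1 randomisation is unbiased on average, and the t-test's standard error already allows for chance imbalance. The variation due to PV status lies within the assumed SD of 20. This stands, and the gain in precision is small.
- **Interpretation.** A reader might infer that without PV status as a stratum, a positive result could not be separated into benefit added to re-isolation and benefit over no ablation. The documents do not support that. PV status is fixed before allocation, so each subgroup comparison is a valid randomised comparison with or without strata.
- **Two different comparisons.** A reader might also infer that the trial mixes two randomised contrasts. In fact re-isolation precedes allocation in both arms, and from then on the contrast is the same: lesion set or no lesion set. What differs by PV status is whether the control procedure includes any ablation, so the effect may differ, but the randomised intervention does not.
- **Prognostic weight.** It is tempting to call PV status the main prognostic factor. Section 1.0 argues that ablation outside the veins may help, but gives no AFEQT difference by PV status. The 5 to 10 points are an assumption.
- **Already handled by section 3.11.** This stands only in part. The rule selects covariates after the data are seen, and PV status is not among the listed parameters.

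**Conclusion.** The point holds as a modest, inexpensive improvement to the design and analysis. It is not a defect of validity. Section 3.12 names no stratification factor in a three-centre trial, although PV status is known before allocation and determines whether a control patient has any ablation.

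Under unrestricted allocation, an imbalance in PV status of more than 10 points has a probability of 9 to 18%, and an imbalance of 10 to 15 points shifts the estimate by 0.5 to 1.5 AFEQT points. Adjustment raises power from 90.0% to between 90.4 and 91.7%. These figures rest on an assumed isolated share (20 to 80% for imbalance, 30 to 50% for power) and an assumed 5 to 10 point difference between PV strata.

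The practical gain is protection against an awkward imbalance, a primary model fixed in advance, and a planned report of the effect by PV status. That report can only be supportive, at 42 to 77% power within a stratum.

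**What to change.** - **Section 3.12:** state that allocation is 1:1, stratified by centre and by PV status at the index mapping (all veins isolated versus at least one reconnected), in permuted blocks of varying size. This gives 3 × 2 = 6 strata, on average 180/6 = 30 patients each.
- **Section 3.6 and the eCRF:** add PV status at the index mapping, recorded before the randomisation call.
- **Section 3.11:** replace the unadjusted t-test, and the adjustment triggered by observed differences, with a pre-specified linear model for change in AFEQT that includes treatment, centre and PV status. Report the treatment effect by PV status and label it supportive.
- **If enrolment has begun:** keep the allocation as it is and make only the eCRF and analysis changes.

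The cost is one eCRF field and slightly more set-up and analysis work. The sample size of 168 evaluable and 180 randomised stays the same.

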## 4.0 RECRUITMENT OF PARTICIPANTS

### 4.1 Consent to participate

As normal clinical praxis, all patients scheduled for AF ablation are seen in the out-patient-clinic 4-6 weeks before the procedure where the medical history is clarified, CT scanning is done and the patients receive information about the procedure. Patients referred to redo procedures for AF (approximately 200 patients) are screened to identify candidates that comply to the inclusion and exclusion criteria. Following information in patient record is used for this screening: age, frequency, symptomatology and duration of AF episodes during the last year, previous ablation procedures and concomitant diseases. This information will be found in the medical record from the last year. This information will be passed-on to the project. Potential candidates will be approached by a study dedicated nurse and under undisturbed conditions, she will provide oral and written information about the study. Written consent form may be signed at this time, later during the day or on the day of the procedure. This ensures that the patient has sufficient time (at least >48 hours) to consider participation and to discuss this with relatives if desired. Another meeting with participation of relatives can be arranged. At any time, participants may withdraw their consent without having to give a reason for this. Patients who decide not to join the study will receive treatment according to current best clinical practice.

Normally, inclusion of 180 patients in the three participating centers will last less than a year.

### 4.2 Insurance

Participants are covered by, at the participating center, standard insurance in case they experience serious adverse events. The options to complain and apply for compensation will be explained in the written information about the study.

## 5.0 ETHICAL ASPECTS

### 5.1 Risks and inconvenience

The duration of the procedure is expected to be approximately 60 minutes longer in the intervention group compared to the control group. However, the majority of complications related to AF ablation, are related to the transseptal puncture, which will be performed in both groups.

In the intervention group, more widespread ablation will take place, potentially increasing the risk of severe complications such as tamponade, stroke, coronary artery lesion, esophageal fistula, phrenic nerve palsy, and conduction disturbances requiring a pacemaker. These complications are rare and reported after less than <0.1% of procedures, including procedures with extensive ablation for PsAF. VOM ethanol ablation carries an increase in the risk of pericarditis and a very small risk (0.4%) of anaphylactic reaction.

## 5.2 Beneficial effects

On an individual level, the participants will be followed more closely than after a standard procedure, accordingly reaction to adverse events and recurrence may be prompt. As hypothesized, the participants in the intervention group may have lower risk of arrhythmias after the procedure compared to standard treatment.

On a population basis, future patients undergoing redo ablation for PsAF, may benefit from results of this study.

## 6.0 BIO BANK

No biological material will be removed from the patient and nothing will be stored for further research during this study.

## 7.0 Data collection, processing, and storage

### 7.1 Monitoring

The investigator will permit trial-related monitoring, audits, IRB/IEC review, and regulatory inspection(s), providing direct access to source data/documents.

### 7.2 Data Collection

Electronic Case Report Forms (eCRFs) will be developed to capture the information outlined in this protocol. Data from these eCRFs will be used in the analysis of study results. Modification of the eCRFs will only be made if deemed necessary by the primary investigators.

All data related to the study will be stored in a REDCAP database administered by Aarhus University in accordance with local regulations including "Databeskyttelsesforordningen" and "Databeskyttelsesloven" and only after approval by local data storage authorities. The data are stored in Denmark and are thereby subjected to Danish legislation. Only the main investigator and one study nurse will have access to the data. Data will be kept until 10 years after completion of the study.

### 7.3 Data reporting

The study nurse and primary investigator are responsible for recording all data from the study on the eCRFs based on source-documented hospital chart reviews.

### 7.4 Source Documentation

Data entered on to the eCRFs will be taken from source documentation, such as hospital procedure reports, admission and discharge summaries, and other hospital or physician office/clinic documents. For some information unique to this study, no standard hospital or office document exists. Therefore, a worksheet will be developed for this purpose, signed by the primary investigator and serve as the source document for those data parameters. These source documents will be used for monitoring the eCRFs. Electronic patient records

will be considered as source documents in general. All eCRFs will undergo manual inspection for omitted data, gross data inconsistencies, and timelines of reporting.

## 7.5 Data update

Regulations require that physicians maintain information in the subject's medical records, which corroborate data collected on the eCRFs. In order to comply with these regulatory requirements, at minimum, the following is a list of information that should be maintained.

Medical history/physical condition of the study subject before inclusion in the study sufficient to verify inclusion criteria (if not already present). Adverse events reported and their resolution, including supporting documents such as discharge summaries, EP lab reports, ECGs, lab results. Study subject's condition upon completion of or withdrawal from the study.

